Participants will be included if they are male or female adults, ≥ 18 to <56 years of age (except ≥ 21 to <56 years of age in Singapore) and ≥ 56 years of age, as long as they do not have underlying conditions that place them at increased risk of severe complications of COVID-19, and who are medically stable such that, according to the judgment of the Investigator, hospitalization within the study period is not anticipated and the individual appears likely to be able to remain on study through the end of protocol-specified follow-up.

Study Design:

This is a multiregional, multicenter, Phase 2, randomized, observer-blind study designed to evaluate the safety, reactogenicity, and immunogenicity of the study vaccine in younger and older adult participants. Enrolled participants will be randomly assigned to receive either study vaccine ARCT-021 or placebo (sterile saline) as the priming vaccination series and ARCT-021, ARCT-154, ARCT-165, or placebo as the booster administration.

Approximately 600 participants (300 younger [≥ 18 to <56 years of age in United States or ≥ 21 to <56 years of age in Singapore] and 300 older [≥ 56 years of age] participants) will be enrolled. At Day 0, participants will be stratified by age and then randomly assigned to one of four groups (3 ARCT-021:1 placebo) to receive 2 doses of study vaccine and/or placebo (see [Synopsis Table 1-1](#) and [Synopsis Figure 1-2](#)) separated by 28 days and, at Day 208, participants will be randomly assigned to ARCT-021, ARCT-154, ARCT-165, or placebo (for Study Groups 1, 2, 3 only) for a third (booster) dose of study vaccine given at 180 days after second study vaccination (Day 208). The randomization ratio of ARCT-021: ARCT-154 : ARCT-165 : placebo will be 1:1:1:1 for Study Groups 1, 2, 3 and the randomization ratio will be 1:1:1 for ARCT-021, ARCT-154, ARCT-165 (no placebo assignment) for any remaining participants in Study Group 4.

Arcturus Therapeutics, Inc.
Protocol ARCT-021-04, Version 6.0

ARCT-021
09 March 2022

Participants who complete study procedures through Day 98 will be offered the opportunity to determine whether they are eligible for study re-enrollment to ensure dosing with ARCT-021. This provides a means of access to active investigational vaccine for those participants who are concerned about their ongoing risk of receiving placebo vaccine during a pandemic.

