The first-in-human study ARCT-021-01 has completed with 106 participants enrolled and vaccinated with either ARCT-021 (N=78) or placebo (N=28). The study was conducted in healthy adult participants in Singapore. At the time of IB version 4.0 finalization, the study report is not final but the available data are summarized in the IB.

Analysis of the open-label extension study ARCT-021-02 has not yet been conducted.

At the time of IB version 4.0 finalization, the present study has completed enrollment of 579 participants. Two interim analyses have been conducted. Across the analyzed clinical experience to date, ARCT-021 has been generally safe and well tolerated at doses ≤ 7.5 μ g. In study ARCT-021-01, the 10- μ g dose tested was associated with more systemic AEs,

Arcturus Therapeutics, Inc.
Protocol ARCT-021-04, Version 6.0

ARCT-021
09 March 2022

including Grade 3 events. In the clinical trials conducted thus far, no vaccine-related SAEs have occurred in ARCT-021-treated participants, and 8 AEs have led to discontinuation.

Most (>90%) ARCT-021-treated participants in each study experienced at least one solicited AE. In each study, the majority of solicited events were Grade 1/mild or Grade 2/moderate. A single participant reported Grade 4 solicited events (dizziness, fatigue, nausea, chills, headache).

The most common solicited AEs were injection site pain, injection site tenderness, headache, fatigue, myalgia, arthralgia and chills. The majority of solicited events had onset on the day after dosing and were no longer reported by the end of 7 days post-dose.

In the ARCT-021-01 study, the overall incidence of solicited events was generally lower in older adults but in the phase 2 study, which represents the largest exposure at clinically relevant doses (ie, 5 µg and 7.5 µg), the incidence was similar between younger and older adults.

Solicited AE reporting appears to decline slightly with second dose of ARCT-021. There may be a slight increase in Grade 3 solicited AE reporting following dosing with 7.5 µg ARCT-021 as compared with 5 µg ARCT-021.

Unsolicited AE reporting is less frequent following ARCT-021 as compared to solicited AEs. The most common unsolicited AEs in both studies include headache, fatigue, injection site tenderness, diarrhea, elevated CPK, neutropenia, lymphopenia, urticaria and hematuria, which was not confirmed on microscopy.

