4 PARTICIPANT SELECTION AND WITHDRAWAL CRITERIA

4.1 Selection of Study Participants

Approximately 600 participants will be enrolled in Singapore and the United States. Participants will be assigned to study vaccine only if they meet all of the inclusion criteria and none of the exclusion criteria.

Participants who withdraw from the study after initial randomization will not be replaced.

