5 STUDY TREATMENTS

5.1 Method of Assigning Participants to Study Groups

Assignment of participants to Study Groups will proceed through the use of an interactive response technology (IRT) system. The site personnel (study coordinator or specified designee) will be required to enter or select information including but not limited to the password, the protocol number, participant age and the participant code (a unique number identifying the participant). The site personnel will then be provided with a vaccine assignment and randomization number. The IRT system will provide a confirmation report containing the participant code, randomization number, and study intervention allocation assigned. The confirmation report must be stored in the site's files.

Additional guidance relating to study vaccine assignment is included in the Investigator Site File.

The Study Group assignments are summarized in [Synopsis Table 1-1](#). Participants enrolled in this study (N=600) will be stratified by age (younger, older; N=300 in each age group). Within each age group, the participants will be randomly assigned to receive ARCT-021 or placebo for the primary vaccination (3:1 randomization ratio), which will consist of 2 injections separated by 28 days (Day 0 and Day 28). At Day 208, participants will be randomly assigned to ARCT-021, ARCT-154, ARCT-165, or (for Study Groups 1, 2, 3 only) placebo for a third (booster) dose of study vaccine given 180 days after second study vaccination (ie, on Day 208). The randomization ratio of ARCT-021, ARCT-154, ARCT-165, and placebo will be 1:1:1:1 for Study Groups 1, 2, 3, and the randomization ratio of ARCT-021, ARCT-154, and ARCT-165 will be 1:1:1 (no placebo assignment) for any remaining participants in Study Group 4.

Participants who complete study procedures through Day 98 will be offered the opportunity to determine whether they are eligible for study re-enrollment to ensure dosing with ARCT-021.

After Day 98 and until Day 198, participants will be contacted to determine whether they are interested, if eligible, in re-enrolling in the study in order to receive active study vaccine.

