3.1. Overall Study Design and Plan

The overall study design is described below. For the final analysis, data for all participants through early termination will be included.

This is a multiregional, multicenter, Phase 2, randomized, observer-blind study designed to evaluate the safety, reactogenicity, and immunogenicity of the study vaccine in younger and older adult participants. Enrolled participants will be randomly assigned to receive either study vaccine ARCT-021 or placebo (sterile saline) as the priming vaccination series and ARCT-021, ARCT-154, ARCT-165, or placebo as the booster administration.

Approximately 600 participants (300 each in younger [≥ 18 to < 56 years of age in United States or ≥ 21 to < 56 years of age in Singapore] and older [≥ 56 years of age] participants) will be enrolled. At Day 0, participants will be stratified by age and then randomly assigned to one of the 4 groups (3 ARCT-021:1 placebo) to receive 2-doses of study vaccine and/or placebo (see Table 3-1) separated by 28 days and, at Day 208, participants will be randomly assigned to active booster vaccine or placebo for a third (booster) dose of study vaccine given at 180 days after second study vaccination (Day 208). At a subset of clinical sites, all enrolled participants will also undergo blood sampling for evaluation of CMI responses. For further details relating to the booster assignments, please refer to the protocol.

Participants who complete study procedures through Day 98 will be offered the opportunity to determine if they are eligible for study re-enrollment to ensure dosing with ARCT-021.

After Day 98 and until Day 198, participants will be contacted to determine whether they are interested, if eligible, in re-enrolling in the study in order to receive active study vaccine. Only participants who are assigned to Study Group 4 (placebo) may re-enroll into the study.

Participants who received ARCT-021 of any dose (Study Groups 1, 2, 3) are asked to remain on the study schedule. Those participants who choose to re-enroll into the study complete early termination procedures and are assigned a new participant number when they re-enter the study. For this interim analysis, the data from re-enrolled participants is not included.

Vaccine doses for primary vaccination will be assigned as shown in Table 3-1.

Table 3-1 **Study Group Assignments**

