9.1.2.1. Unsolicited AEs through 28 Days Post Each Vaccination

Summaries of unsolicited AEs through 28 days post each vaccination dose will be presented using the following definition:

- **Vaccination 1:** Time period from first vaccination through prior to the second vaccination for participants that received the second vaccination and through 28 days following the first vaccination for participants that did not receive the second vaccination
- **Vaccination 2:** Time period from second vaccination through 28 days following the second vaccination
- **Booster Vaccination:** Time period from booster vaccination through 28 days following the booster vaccination.

The summaries for Vaccination 1 and Vaccination 2 will be by the 4 priming vaccination treatment groups for the priming vaccination period while the summaries for booster vaccination period will be by the 8 priming-booster vaccination treatment groups and for the combined E1+E2+...+G1+G2 and H1+H2 groups (Table 4-1).

For re-enrolled subjects, the above summary for the priming vaccination phase will be repeated.

An overall summary of unsolicited AEs through 28 days post vaccination will be produced for all participants and by age group including the number and percentage of participants with any of the following (including 2 sided 95% CIs using the Clopper-Pearson method):

- Any unsolicited TEAEs
- Any severe unsolicited TEAEs
- Any unsolicited TEAEs that are treatment related

- Any severe unsolicited TEAEs that are treatment related
- Any serious TEAEs
- Any treatment-emergent MAAEs
- Any treatment-emergent NOCDs
- Any TEAEs leading to discontinuation/withdrawal
- Any TEAEs leading to death

In addition, incidence of unsolicited AEs through 28 days post each vaccination will be summarized by SOC and PT including number and percentage of participants with an event for all participants and by age group for the following:

- All unsolicited AEs
- All unsolicited AEs by severity
- All unsolicited AEs by relationship to treatment

For re-enrolled subjects, the above summaries will be repeated for the Safety set. A summary of incidence of unsolicited adverse events up to 28 days post booster vaccination with active boosters pooled will be presented.

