9.1.2.2. Unsolicited AEs by Time Period

Summaries of unsolicited AEs by time period will be presented using the following definition:

- **Prior to Booster Vaccination** summary tables include the following time periods with data summarized by the 4 priming vaccination treatment groups:
 - **Vaccination 1 through prior to Vaccination 2:**

- For participants who receive vaccination 2, this is the time period from first vaccination through prior to second vaccination
- For participants who do not receive vaccination 2 but do receive a booster vaccination, this is the time period from first vaccination through prior to the booster vaccination
- For participants who only received the first vaccination, this is the time period from first vaccination until early termination or end of the priming period (Day 207), whichever is earlier
- **Vaccination 2 through prior to Booster Vaccination:**
 - For participants who receive the booster vaccination, this is the time period from the second vaccination through prior to the booster vaccination
 - For participants who do not receive the booster vaccination, this is the time period from second vaccination until early termination or end of the priming period (Day 207), whichever is earlier
- **Prior to Booster Vaccination - Overall**
 - This is the time period from first vaccination through prior to booster vaccination. For participants who do not receive a booster vaccination, this is the time period from first vaccination through early termination or end of the priming period (Day 207), whichever is earlier.
- **Post Booster Vaccination through Early Termination** summary tables include data summarized by the 8 priming-booster treatment groups as well as a summary for the combined E1+E2+...+G1+G2 and H1+H2 groups. For subjects who do not receive a booster vaccination, this is the time period from the start of the booster period (Day 208) through early termination.
 - An overall summary of unsolicited adverse events post booster vaccination with active boosters pooled (as presented in Table 4-1; e.g., A1, A2, B1, B2, etc.) will also be presented.

The summaries described in [Section 9.1.2.1](#) will be produced by time period and by time period and age group. In addition, the following summaries will be presented by time period and by time period and age group:

- Overall summary and incidence of treatment emergent MAAE
- Overall summary and incidence of treatment emergent NOCDs

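### The combined active-booster and placebo/no-booster AE columns mix priming histories, so reading them side by side does not give a booster effect

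*SAP*

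**What the plan says.** Booster allocation depends on priming. For ARCT-primed participants, Protocol Synopsis (Study Design) states: "The randomization ratio of ARCT-021: ARCT-154 : ARCT-165 : placebo will be 1:1:1:1 for Study Groups 1, 2, 3". For placebo-primed participants who did not re-enrol, Protocol 5.1 states that the ratio "will be 1:1:1 (no placebo assignment) for any remaining participants in Study Group 4". SAP Table 3-1 repeats both rules.

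SAP Table 4-1 crosses priming with booster to give eight groups. E1, F1 and G1 are ARCT-primed participants given ARCT-021, ARCT-154 and ARCT-165; E2, F2 and G2 are their placebo-primed counterparts. H1 is ARCT-primed with a placebo booster or none. H2 is placebo-primed with no booster.

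For the 28-day post-booster tables, SAP 9.1.2.1 presents unsolicited AEs "by the 8 priming-booster vaccination treatment groups and for the combined E1+E2+...+G1+G2 and H1+H2 groups". For the tables running to early termination, SAP 9.1.2.2 has data "summarized by the 8 priming-booster treatment groups as well as a summary for the combined E1+E2+...+G1+G2 and H1+H2 groups". Neither section stratifies, weights or qualifies the combined columns.

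SAP 4.4.9 analyses booster safety by vaccine actually received, and counts anyone unboosted but with booster-period safety data in the placebo booster group. The booster safety objective (SAP 2.3, exploratory) is framed as active boosters versus placebo.

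**The concern.** Placed together under a versus-placebo objective, the two combined columns invite subtraction. That subtraction would compare populations with different vaccine histories. Placebo-primed people in the active column are having their first active dose, whereas ARCT-primed people are having a repeat dose. The ARCT-primed recipients have also been filtered for tolerance, because Protocol 4.2.2 bars further dosing after events such as a confirmed Grade 3 solicited AE. Any placebo-primed person in the control column is there because a booster was missed, not because placebo was assigned.

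Priming could plausibly affect AE rates. Protocol 1.5 reports: "Solicited AE reporting appears to decline slightly with second dose of ARCT-021". It also says that overall AE reporting may fall at the second vaccination. At stake is the one booster safety display that combines all priming groups into an active column and a control column.

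**Working it through.** **Plan's own figure.** SAP Table 4-2 gives a 22.2% chance of seeing at least one event of 1% incidence in a booster group of 25. The formula reproduces it: 1 - (1 - 0.01)^25 = 0.222. All 30 cells of the table reproduce. The plan gives no figure for the combined columns.

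**Inputs from the documents.** Protocol 4.1: "Approximately 600 participants will be enrolled in Singapore and the United States". Priming is 3:1, so 600 x 3/4 = 450 ARCT-primed and 600 x 1/4 = 150 placebo-primed. The booster is active for 3/4 of the ARCT-primed and for all of the placebo-primed. Re-enrolled Group 4 participants are reported separately (Protocol 7.6.7), so they leave the placebo-primed pool.

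**Assumptions, because the documents give no figures.** Re-enrolment of Group 4 is 0 to 75%; placebo-primed left unboosted, 0 to 50%; ARCT-primed left unboosted, 0 to 25%.

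**Composition with everyone boosted and no re-enrolment.** Active: 450 x 0.75 = 337.5 ARCT-primed plus 150 placebo-primed, so the placebo-primed share is 150/487.5 = 30.8%. Control: 450 x 0.25 = 112.5 ARCT-primed plus 0, a share of 0%. The 30.8% follows from the ratios alone and does not depend on total N.

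**Shift under no booster effect.** Let r_P and r_A be the AE rates in placebo-primed and ARCT-primed participants, whether boosted or not, and s the placebo-primed share of a column. Then

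pooled difference = (r_P - r_A) x (s_active - s_control).

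Illustration with r_A = 20% and r_P = 30%: active = (337.5 x 0.20 + 150 x 0.30)/487.5 = 23.1%, control = 20.0%, difference +3.1 points although the booster does nothing in either group. If the two rates are exchanged, the difference is -3.1.

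Selected scenarios, per assumed 10-point gap (r_P above r_A):

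| Group 4 re-enrolled | Placebo-primed unboosted | ARCT-primed unboosted | Active (ARCT + placebo-primed) | s_active | H1 + H2 | s_control | Shift, points |
|---|---|---|---|---|---|---|---|
| 0% | 0% | 0% | 337.5 + 150 | 30.8% | 112.5 + 0 | 0% | +3.1 |
| 50% | 0% | 0% | 337.5 + 75 | 18.2% | 112.5 + 0 | 0% | +1.8 |
| 75% | 0% | 0% | 337.5 + 37.5 | 10.0% | 112.5 + 0 | 0% | +1.0 |
| 0% | 0% | 25% | 253.1 + 150 | 37.2% | 196.9 + 0 | 0% | +3.7 |
| 0% | 25% | 0% | 337.5 + 112.5 | 25.0% | 112.5 + 37.5 | 25.0% | 0.0 |
| 0% | 50% | 0% | 337.5 + 75 | 18.2% | 112.5 + 75 | 40.0% | -2.2 |

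The fourth and last rows are the extremes over the assumed ranges. The shift vanishes only by coincidence, for example when the unboosted share of the placebo-primed happens to equal the one-in-four placebo allocation of the ARCT-primed.

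The formula ties the gap to priming status. If the gap is purely a reaction to a first active dose, unboosted H2 participants do not carry it and the shift is s_active x gap. On the same ranges that is 18.75/356.25 = 5.3% to 37.2%, or 0.5 to 3.7 points per 10. The documents do not say which description applies.

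**Within ARCT-primed participants.** E1+F1+G1 against the ARCT-primed placebo allocation is 337.5 against 112.5 with no placebo-primed on either side, so the shift from priming is zero.

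**A related gap.** SAP 9.1.2.1 starts the 28-day window at the booster injection, so unboosted participants have no defined window there. SAP 9.1.2.2 gives them one, from Day 208.

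**The case against.** The best defence is that the SAP plans no contrast. It specifies counts, percentages and per-column intervals, and Protocol 7.2 and 7.6.1 rule out hypothesis testing and describe the analysis as descriptive. That stands, and it limits the weight of the point.

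A reader might infer that priming-specific results are missing. They are not. The eight groups appear in the same tables, and the second layout in SAP section 4 pools active boosters within priming regimen (A1/A2 to D1/D2). SAP 9.1.2.2 requires that layout for the overall post-booster summary, and 9.1.2.1 also calls for an incidence summary with active boosters pooled. D1 is in substance E2+F2+G2. What is absent is the single ARCT-primed active column with its own interval, and a control column confined to participants who received placebo.

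A reader might also infer that E1+F1+G1 against H1 as defined is a clean randomised comparison. It is not: H1 includes unboosted participants under SAP 4.4.9, and ARCT-primed people barred from further dosing who stay in follow-up can fall there.

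The evidence that priming matters is thin for these tables. The cited decline is slight and concerns solicited events, which reach unsolicited tables only if they last beyond 7 days or meet MAAE, NOCD, SAE or discontinuation criteria (Protocol 6.4.1.1.1). The effect is plausible but not quantified.

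Finally, an all-active total has a use. With 22.2% detection of a 1% event at N=25, pooling helps to find rare events, so the column need not be removed.

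**Conclusion.** The point holds as a defect in an exploratory, descriptive safety summary. The combined columns mix priming histories, only one priming group could be randomised to placebo, and nothing in SAP 9.1.2.1 or 9.1.2.2 warns the reader. Their difference is not a booster effect.

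The imbalance is 30.8 percentage points in placebo-primed share at planned allocation with full boosting and no re-enrolment, and +37 to -22 points over the assumed ranges. It is tempting to say that the active column is inflated by about 2 to 3 points. The documents do not support that: it needs an assumed 10-point gap and an empty H2, and re-enrolment, the unboosted share and AE rates by priming are not given. Neither size nor sign is established. No primary analysis is affected.

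The conclusion rests on the booster allocation in the design text and in SAP Tables 3-1 and 4-1. Footnote b of the priming schedule of events in both documents instead has Group 4 receiving placebo at Day 208 without booster randomisation. These passages contradict each other and must be reconciled.

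**What to change.** In the booster tables of SAP 9.1.2.1 and 9.1.2.2:

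- Add an E1+F1+G1 column, with its Clopper-Pearson interval wherever the table gives intervals.
- Split H1. Set E1+F1+G1 against ARCT-primed participants randomised to and given placebo booster, and show ARCT-primed participants with no booster in a separate column.
- Show E2+F2+G2 in its own column, labelled as first active exposure with no randomised comparator.
- Keep E1 to G2 only as an all-active exposure total for rare events, with a footnote that it mixes priming histories and is not comparable with H1+H2.

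This changes table shells only and needs no new data. The cost is a few more columns and smaller numbers in each.

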9.1.2.2. Unsolicited AEs by Time Period

Summaries of unsolicited AEs by time period will be presented using the following definition:

- **Prior to Booster Vaccination** summary tables include the following time periods with data summarized by the 4 priming vaccination treatment groups:
 - **Vaccination 1 through prior to Vaccination 2:**

- For participants who receive vaccination 2, this is the time period from first vaccination through prior to second vaccination
- For participants who do not receive vaccination 2 but do receive a booster vaccination, this is the time period from first vaccination through prior to the booster vaccination
- For participants who only received the first vaccination, this is the time period from first vaccination until early termination or end of the priming period (Day 207), whichever is earlier
- **Vaccination 2 through prior to Booster Vaccination:**
 - For participants who receive the booster vaccination, this is the time period from the second vaccination through prior to the booster vaccination
 - For participants who do not receive the booster vaccination, this is the time period from second vaccination until early termination or end of the priming period (Day 207), whichever is earlier
- **Prior to Booster Vaccination - Overall**
 - This is the time period from first vaccination through prior to booster vaccination. For participants who do not receive a booster vaccination, this is the time period from first vaccination through early termination or end of the priming period (Day 207), whichever is earlier.
- **Post Booster Vaccination through Early Termination** summary tables include data summarized by the 8 priming-booster treatment groups as well as a summary for the combined E1+E2+...+G1+G2 and H1+H2 groups. For subjects who do not receive a booster vaccination, this is the time period from the start of the booster period (Day 208) through early termination.
 - An overall summary of unsolicited adverse events post booster vaccination with active boosters pooled (as presented in Table 4-1; e.g., A1, A2, B1, B2, etc.) will also be presented.

The summaries described in [Section 9.1.2.1](#) will be produced by time period and by time period and age group. In addition, the following summaries will be presented by time period and by time period and age group:

- Overall summary and incidence of treatment emergent MAAE
- Overall summary and incidence of treatment emergent NOCDs
- Incidence of treatment emergent serious AEs
- Incidence of treatment emergent AEs leading to discontinuation/withdrawal

Individual participant adverse event data will be provided in data listings for the following:

- All unsolicited adverse events
- Serious unsolicited adverse events
- Medically attended adverse events (MAAE)
- New onset of chronic disease (NOCD)
- Adverse events leading to discontinuation/withdrawal

In addition, overall summary and incidence of unsolicited adverse events prior to booster vaccination by time period and age group (≥ 18 to <65 years; ≥ 65 years) for Safety analysis set will provided.

